Cover Page

Title: Brief Protocol Summary-- Addressing Intersectional Stigma: Testing THRIVE 365 for Black Sexual Minority Men (On The Daily)

NCT Number: NCT05376397

Document Date: 12/18/2023

Brief Protocol Summary

The sample consisted of Black sexual minority men (SMM) living with HIV and connected with the community-based organization, THRIVE SS. THRIVE SS is an Atlanta, GA based CBO that focuses on health equity for Black SMM, most of whom are living with HIV, through cultivating peer support, advocacy, and community building. The study team recruited a nonrandom purposive sample through advertisements on THRIVE SS's social media and email blasts. Eligibility criteria for this analysis were: 16 years old or older, identifying as masculine, identifying as Black/African American, reporting being attracted to and/or sexually active with men, able to complete all procedures in English, mobile access to the internet in order to complete the once-daily survey procedures. After the screening eligible for the study, participants received an invitation to participate in a HIPPA compliant WebEx informed consent meeting and baseline assessment with a trained research assistant. After baseline was a 14-day daily diary study with surveys administered on an Internet-based Qualtrics platform. Across all days, participants received 8 PM text-messages with links to their daily surveys. For those who had not completed the survey by 9:30 PM, they received an automatic reminder message. Surveys included measures of psychological and behavioral variables. We used simple randomization to vary the order of administration of all instruments. In line with a pre-post, one-arm trial, participants did not have access to the iTHRIVE 365 intervention for days 1–7 then received access to register and use the invention for days 8–14. The follow-up assessment occurred at the end of the 2-week daily diary period. We collected summary paradata (i.e., process data detailing app usage) on intervention page access. Participants received \$30 for baseline and follow-up and \$1.50 per survey for the first 7 daily surveys and \$2.50 for the next 7 surveys, with a \$5 bonus for completing all surveys (total maximum: \$93). The Rutgers University institutional review board approved all study procedures.

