Specifically, we will examine associations between iTHRIVE 365 engagement and next day outcomes with a multilevel vector autoregressive models (VAR (1)) in the DSEM framework.⁴² All models will adjust the effects of engagement for app availability since app registration occurred starting on day 8 of the study. As an example, the models examining the association between iTHRIVE 365 engagement (T365) and depressive symptoms (Dep) can be written in statistically as

$$\begin{aligned}
 & \text{Within-Person} \\
 & \text{Dep}_{ti} = \alpha_{1i} + \varphi_{1i} \text{Dep}_{(t-1)i}^C + \beta_{1i} \text{T365}_{(t-1)i} + e_{1ti} \\
 & \text{T365}_{ti} = \nu_1 + \varphi_2 \text{T365}_{(t-1)i} + \beta_2 \text{Access}_{ti} \\
 & \text{Between-Person} \\
 & \alpha_{1i} = \gamma_{00} + u_{0i} \\
 & \beta_{1i} = \gamma_{10} + u_{1i} \\
 & \varphi_{1i} = \gamma_{20} + u_{2i}
 \end{aligned} \tag{1}$$

With distributional assumptions,

$$\begin{aligned}
 \mathbf{e}_i & \sim N \left(\mathbf{0}, \text{diag} \left[\sigma_1^2, \sigma_2^2 \right] \right) \\
 \mathbf{u}_i & \sim N \left(\mathbf{0}, \begin{bmatrix} \tau_{00} & & \\ \tau_{21} & \tau_{11} & \\ 0 & 0 & \tau_{22} \end{bmatrix} \right)
 \end{aligned} \tag{2}$$

In the first expression in the within-person equation, Dep is the depressive symptoms outcome, t indexes time (in days, $t = 1, \dots, 14$), i indexes individuals ($i = 1, \dots, N$), α_{1i} is a person-specific intercept for depressive symptoms, φ_{1i} is the autoregressive effect capturing the carryover of depressive symptoms from the previous day to the current day, Dep^C is latent-centered depressive symptoms such that $\text{Dep}_i^C = \text{Dep}_i - \alpha_{1i}$ (latent centering helps alleviate Ludkte's and Nickell's bias in time-series models),⁴³ β_{1i} is a time-varying covariate effect of T365 access the previous day on depressive

symptoms during the current day, and e_i is a normally distributed within-person error with variance σ_1^2 . The second expression in the within-person equation is a probit model because T365 use is dichotomous such that ν_1 is the threshold for T365 use, φ_2 is the carryover effect of T365 use the previous day onto T365 use during the current day, and β_2 accounts for whether person i had access to the intervention at time t .

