In the between-person model, γ are fixed effects that capture the average effect of the parameter across all persons, and u are normally distributed random effects capturing person-specific deviations from the fixed effects. The variances of the random effects are captured by the diagonal elements of the tau-matrix; one random effect covariance between depressive symptoms intercepts and the lagged T365 effect is also estimated as denoted by the τ_{10} element in the off-diagonal. Figure 1 features a path diagram for this model.

In line with best practice recommendations for DSEM with small sample sizes,⁴⁴ we will use range restricted priors of $Uniform[0,1]$ for the random effect variances τ_{00} , τ_{11} , and τ_{22} to stabilize the sampling in the MCMC optimization. This approach does not encode subjective prior beliefs but rather just limits the prior's support to range of values that the outcome can take. *Mplus* default priors were used for other parameters that are minimally influenced by sample size including improper $N(0, \infty)$ for regression paths or random effect covariances and improper $InvGamma(-1, 0)$ for within-person error variances. Parameters will be estimated via Markov Chain Monte Carlo with a Gibbs sampler using two chains thinned by 10 iterations with a minimum of 20,000 iterations. Convergence after 20,000 iterations was evaluated using the potential scale

reduction method using a threshold of $\hat{R} \leq 1.10$. We will compute credible intervals with the highest posterior density method.

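### Because the app is withheld on days 1–7, the data set no upper limit on the Access coefficient in the T365 probit, so its posterior is either improper or set by a threshold prior the SAP does not state

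*SAP*

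**What the plan says.** The Protocol (Brief Protocol Summary) states that "participants did not have access to the iTHRIVE 365 intervention for days 1–7 then received access to register and use the invention for days 8–14". Likewise, the SAP (Analytic Plan) says that "app registration occurred starting on day 8 of the study".

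The second within-person line of equation (1) regresses T365 on its previous-day value (φ₂) and on Access (β₂), with no random effects. The SAP says this line "is a probit model because T365 use is dichotomous", that ν₁ "is the threshold for T365 use", and that β₂ "accounts for whether person i had access to the intervention at time t". Time runs over all 14 days, and nothing limits this line to days with access.

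On priors, the SAP bounds the random-effect variances and then says that Mplus "default priors were used for other parameters that are minimally influenced by sample size". Its list of these defaults begins with "improper $N(0, \infty)$ for regression paths or random effect covariances". That covers β₂ and φ₂. The SAP calls ν₁ a threshold, not a path, and writes out no prior for it.

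Convergence is judged by R-hat ≤ 1.10 with two chains, thinning by 10 and at least 20,000 iterations; no parameter is exempted. The SAP also proposes to form a 95% credible interval for each parameter and to read exclusion of 0 as the counterpart of significance. It mentions neither separation nor a remedy for it.

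**The concern.** A probit learns the effect of Access by comparing use on days with and without it. Here use without access is impossible by design, so the comparison is between some use and none at all. Any sufficiently large β₂, offset by an equally lower ν₁, fits the data equally well. The SAP places β₂ among the parameters that sample size hardly affects, but more men only add more certain zeros.

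Three things are at stake. First, a reported ν₁ or β₂ would have no meaning beyond its prior, yet β₂ would look significant under the SAP's interval rule simply because the app was withheld. Second, an R-hat rule with no exempt parameters can fail, or pass by accident, because of this pair. If the other outcomes follow the depressive-symptoms example, the same line recurs in every psychological outcome model. Third, β₂·Access is the only availability term in equation (1), and the SAP commits all models to adjust for availability.

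**Working it through.** **1. Inputs.** From the documents: no access on days 1–7, access on days 8–14, a probit with terms ν₁, φ₂ and β₂, a flat prior on paths, and the MCMC rule above. After taking the lag, each man gives 6 no-access days (2–7) and 7 access days. The documents give neither the number of men nor the rate of use. Assumed: N = 20, 50, 100 and daily use of 0.1, 0.3, 0.6 once access opens. The threshold prior is taken as flat or N(0, v) with v = 1, 5, 25, 100. The SAP states no figure on this point to reproduce.

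**2. Separation.** A linear-programming check on simulated data found quasi-complete, not complete, separation in all 9 scenarios. Lowering ν₁ and raising β₂ by the same amount never lowers the likelihood. Access days still contain both uses and non-uses.

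**3. Likelihood.** On days 2–7 lagged use is also 0, so the no-access days contribute 6N·ln Φ(−ν₁). Access days depend only on ν₁ + β₂ and φ₂. With N = 50 (300 no-access days), the contribution is:
- ν₁ = −2: 300 × ln Φ(2) = −6.90
- ν₁ = −3: 300 × ln Φ(3) = −0.41
- ν₁ = −4: 300 × ln Φ(4) = −0.0095
- ν₁ = −5: 300 × ln Φ(5) = −0.00009

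It rises to 0 and never turns down. The full profile log-likelihood (N = 50, use 0.3) is −226.73 at β₂ = 2, −224.85 at 4, and −224.8484 at every value tried from 5 to 40. There is no finite maximum.

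**4. Posterior, ν₁ flat.** Leave out the lag term and put s = ν₁ + β₂. With β₂ flat, s integrates out to a constant, leaving p(ν₁ | data) ∝ π(ν₁)·Φ(−ν₁)^(6N). With π constant and N = 50, the mass above −B is 7.1, 97.1, 997.1 and 9997.1 for B = 10, 100, 1000 and 10000. It grows as B − 2.9, without limit, so the joint posterior is improper.

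**5. Posterior, ν₁ ~ N(0, v), β₂ still flat.** The same integral is finite: 0.0033, 0.102, 0.283 and 0.387 for v = 1, 5, 25, 100. The posterior is proper.

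**6. Sampler.** Two-chain probit Gibbs, N = 50, use 0.3, 20,000 unthinned iterations, R-hat on the second half, 10 chain pairs. Ranges are pooled percentiles, not highest-density intervals.

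| Prior on ν₁ | Pairs with R-hat ≤ 1.10 for β₂ | 95% range of β₂ |
|---|---|---|
| flat | 1 of 10 (R-hat 1.00 to 3.83) | no stable range |
| N(0, 1) | 10 of 10 | 1.75 to 3.32 |
| N(0, 5) | 9 of 10 | 2.04 to 6.21 |
| N(0, 25) | 6 of 10 | 2.31 to 11.53 |
| N(0, 100) | 4 of 10 | 2.54 to 17.65 |

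Under every prior, ν₁ + β₂ had median −0.48 (95% range −0.64 to −0.32) and R-hat for φ₂ was 1.00.

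A second run with both priors flat used thinning by 10, 50 men, about 39% use and four chain pairs. R-hat for β₂ was 6.87, 1.03, 1.55 and 1.02 at 20,000 iterations, and 1.03, 1.31, 1.81 and 1.80 at 200,000. Two passes became failures and one failure became a pass. The pooled 95% range of β₂ moved from 2.6–29 to 4.4–62.

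**7. Engagement effect.** In equation (1), lagged T365 enters the depressive-symptoms line as a covariate and the errors are independent. With T365 observed, the likelihood factorises, and γ₁₀ does not depend on β₂.

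**The case against.** The strongest reply is that β₂ is a nuisance term. The stated aim is the association between engagement and next-day outcomes, which is carried by β₁ᵢ and γ₁₀, and no hypothesis attaches to β₂. That stands: step 7 shows the engagement effect is untouched, and R-hat for the outcome parameters remains informative. A reader might infer that the outcome results are invalid; the documents do not support that.

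A reader might also infer that the stated flat prior alone leaves no proper posterior and that the convergence rule cannot be met. Neither follows. The flat prior is stated for paths, the threshold's prior is not written out, and any proper normal prior on ν₁ makes the posterior proper. With N(0, 1) every chain pair passed. The 20,000 iterations are also a minimum, so slow mixing under a proper prior can be met with longer runs. Nor is the separation perfect, since access days contain both outcomes.

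Engagement is partly self-reported, so a mistaken report of use on a no-access day would break the separation. That is possible, but β₂ would then rest on reporting errors.

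Finally, day 8 carries a lagged zero that the design forces. A reader might infer that this distorts φ₂. No such effect has been shown, and an R-hat of 1.00 speaks to mixing, not bias. It is not part of this point.

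What remains is a parameter that the design cannot bound, given a flat prior, with no exemption from the interval and convergence rules.

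**Conclusion.** The point holds, conditionally on the threshold prior. No sample size sets an upper limit on β₂. With ν₁ flat, the joint posterior of (ν₁, β₂) is improper and an R-hat pass is an accident. With ν₁ proper, the posterior is proper, but the unstated prior fixes the size and interval of β₂: the upper limit rises about fivefold (17.65 / 3.32 = 5.3) between v = 1 and v = 100, and convergence slows as the prior widens.

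The harm is limited to any reported ν₁ or β₂ and to a convergence statement that covers all parameters.

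The separation follows from the design, given no mistaken self-report of use on days 1–7. The sampler figures assume 50 men and the use rates shown. The protection of γ₁₀ assumes observed T365 and an observed lag, as equation (1) is written. The stability of φ₂ was seen in the 50-man runs. In the sparsest scenario (20 men, 9 uses in all) the separating direction also lowered φ₂, which is a sparse-data matter apart from this point.

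**What to change.** Choose one of two changes and write it into the Analytic Plan:

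- **Proper priors.** State proper priors for both ν₁ and β₂, and say that β₂ is not interpreted. Check that the chosen priors do not move ν₁ + β₂.
- **Access days only.** Fit the T365 line on days 8–14, with the lagged-use term from day 9, and drop β₂·Access. In the outcome line, enter T365 on days 1–7 as a known zero. The commitment that all models adjust for app availability must then be revised, because its only term in equation (1) has gone.

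In either case, say which parameters the R-hat rule covers.

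The cost is a short SAP edit and a small change to the model code, plus a refit if models have already been run; the SAP's past tense on convergence leaves that open. No information about use is lost, since days 1–7 carry none.

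### Does the Uniform[0,1] cap on the random-effect variances need to be reset to each outcome's score range?

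*SAP*

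**What the plan says.** The SAP's Analytic Plan models each psychological outcome with a random intercept (variance τ₀₀), a random effect of the previous day's iTHRIVE 365 use (τ₁₁) and a random autoregression (τ₂₂); see equations (1) and (2). One depressive-symptom model is written out to stand for the rest: "As an example, the models examining the association between iTHRIVE 365 engagement". On priors, the SAP says "we will use range restricted priors of" Uniform[0,1] for all three variances, and gives the purpose as "to stabilize the sampling in the MCMC optimization". It adds that "This approach does not encode subjective prior beliefs" and that the restriction only confines the prior's "support to range of values that the outcome can take". The remaining priors are flat software defaults. An effect counts as established when its 95% credible interval excludes 0.

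The Protocol's Brief Protocol Summary does not name the daily instruments. Neither document gives a score range, an item count or a rescaling rule.

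**The concern.** A variance carries squared units. Multiplying a score by c multiplies τ₀₀ and τ₁₁ by c², while τ₂₂ does not change. A fixed cap of 1 is therefore generous on a 0–1 score and can be severe on a raw sum score. The SAP justifies the cap by the outcome's range without giving that range, so a reader cannot check the claim that the prior is neutral.

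What could be at stake is the interval for γ₁₀, the average effect of use on the next day's outcome. If τ₁₁ is held below its true value, the part of γ₁₀'s uncertainty that comes from differences between people is understated. The interval is then too short and may exclude 0 too often. The reported between-person variances would be too small as well.

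**Working it through.** **The plan's own figure.** A quantity confined to an interval of width W has variance at most W²/4. Let R be the outcome's score range.

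- Intercepts: W = R, so τ₀₀ ≤ R²/4. This equals 1 at R = 2.
- Effects of a 0/1 predictor lie in [−R, R], so W = 2R and τ₁₁ ≤ R². This equals 1 at R = 1.
- Stationary autoregressions lie in (−1, 1), so W = 2 and τ₂₂ ≤ 1 on any scale.

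The cap of 1 is thus reproduced for τ₂₂. For the other two it cannot be derived, because R is not given. The τ₁₁ limit assumes that lagged use enters as observed 0/1. The SAP's equation for use "is a probit model because T365 use is dichotomous"; if its latent response is the predictor, the c² argument still holds but this limit does not.

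**Worst case against likely case.** Those limits need half the participants at each extreme. The SAP instead assumes that the u terms "are normally distributed random effects capturing person-specific deviations from the fixed effects". If the random-effect SD is a share s of the range, the variance is (sR)² and reaches 1 at R = 1/s.

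| Variance | SD as share of range | R at which it reaches 1 |
|---|---|---|
| τ₀₀ | 10%, 15%, 20%, 25% | 10, 6.7, 5, 4 |
| τ₁₁ | 5%, 10%, 15% | 20, 10, 6.7 |

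Person means spread evenly over the scale have variance R²/12, which passes 1 only above R = √12 ≈ 3.5.

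**Effect on γ₁₀.** The outcome equation was simulated with no mean effect. All inputs are assumed: N = 50; use on half of the accessible days; intercept, slope and within-day SDs of 20%, 10% and 15% of the range; 15% of days missing; 600 data sets. The Monte Carlo standard error at 5% is √(0.05 × 0.95/600) = 0.9 points. With outcomes rescaled to 0–1, 5.0% of intervals excluded 0 (30 of 600).

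| R under the cap of 1 | False positives | Interval width relative to 0–1 rescaling | Newly / no longer excluding 0 |
|---|---|---|---|
| 4 | 4.8% | 1.00 | 0 / 1 |
| 6 | 5.7% | 0.97 | 4 / 0 |
| 10 | 6.8% | 0.90 | 14 / 3 |
| 20 | 9.8% | 0.82 | 31 / 2 |

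At R = 10, 30 + 14 − 3 = 41 of 600, with an exact 95% interval of about 4.9% to 9.2%, which includes 5%. The paired count does show that the cap shortens intervals there: for 3 or fewer of 17 one way, the two-sided probability is 2 × (1 + 17 + 136 + 680)/2¹⁷ = 0.013. It does not show that they fall below nominal coverage.

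**Sensitivity** (400 data sets per case, 300 for N = 100; Monte Carlo SE about 1.1 to 1.7 points).

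| Case | Rescaled to 0–1 | Cap, R = 10 | Cap, R = 20 |
|---|---|---|---|
| Slope SD 15% of range | 4.5% | 10.5% | 13.5% |
| Slope SD 5% of range | 3.5% | 3.8% | 5.5% |
| N = 30 | 3.0% | 4.8% | 8.8% |
| N = 100 | 3.7% | 5.0% | 8.7% |
| Mean at 30% of range | 2.8% | 4.3% | 7.0% |

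At R = 10 the cap is at or below 5% in four of five cases. In those four it is nearer 5% than rescaling is (distances 1.2, 0.2, 0.0 and 0.7 points against 1.5, 2.0, 1.3 and 2.2), although single differences are close to Monte Carlo error.

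**What a change would do to the prior.** On a 0–1 scale the assumed variances are 0.20² = 0.04 and 0.10² = 0.01. A cap of 1 is then 1/0.04 = 25 and 1/0.01 = 100 times larger, so it restricts little and gives up most of the stabilisation that the SAP wants from it.

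**The case for a change.** The best case for a change is that the result should not depend on an arbitrary choice of units. In the simulation, the same answers scored 0–4 (a five-item mean) or 0–20 (the sum) led to different conclusions in 34 of 600 data sets (5.7%). At R = 20 the posterior median of τ₀₀ was 0.75 under the cap against 14.4 without it. A closed-form calculation that holds τ₁₁ at the cap gives the same width ratio at R = 20 (0.82) and about 11% false positives. With a slope SD of 15% of the range at R = 20 it gives 20%, against 13.5% simulated. Rescaling takes one line per outcome, and the other stated priors are flat, so they would stay flat.

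The algebra stands, and so does the mechanism on wide scores with sizeable slope variation. So does the complaint that the link to the outcome's range cannot be checked from the documents.

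Three parts do not stand:

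- Nothing places this trial's outcomes on wide scores. A 0–20 raw sum would sit badly with the SAP's own sentence about range, so that sentence points to narrow scoring.
- Stating the scoring would make the rationale checkable, not true. For a 0–4 score the formal maxima are 4²/4 = 4 for τ₀₀ and 4² = 16 for τ₁₁, yet the simulated effect at R = 4 was nil.
- The substantive remedies have a cost. Wider limits stabilise the sampler less, and power was not simulated. A check for posterior draws near the bound (more than 5% of τ₀₀ draws in the top tenth) would have flagged 37% of fits at R = 4 and 99% at R = 6, where the γ₁₀ interval hardly moves.

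**Conclusion.** No change to the plan follows. The SAP omits the scoring that would let a reader verify its cap, but it does say the cap reflects the outcome's range, and analysts who know the scoring can apply it sensibly. If the outcomes are scored 0–1, the cap excludes nothing attainable. Up to about 4 to 6 points it has little or no effect on γ₁₀ under the assumed inputs. At 10 points the main-case rate of 6.8% cannot be told from 5%. Material excess needs roughly a 20-point score (5.5% to 13.5% across the cases run), or 10 points with a slope SD of 15% of the range (10.5%).

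These percentages illustrate a mechanism. N, use rate, SDs and missingness are all assumed, and lagged use is taken as observed 0/1; they do not estimate this trial's error rate. The trial is also a one-arm pilot whose SAP lists feasibility and acceptability first. The choice between a tight cap and a loose one is a fair trade-off of sampler stability against possible truncation. A sentence on scoring beside the prior would help readers, but it is optional.
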